3.3. Discussion of study design, including the choice of control groups

The study has a parallel group design, which is deemed more appropriate than a cross-over considering the aetiology of the illness. Patients will be randomised, in equal proportions, to placebo or the active dose regimen.

Bias is controlled through a placebo group.

4. PATIENT SELECTION CRITERIA

4.1. Patient recruitment

Patients will be recruited from the population of outpatients at the study sites. Patients may also be recruited by other methods such as clinic lists, research registers, and patients learning about the study from websites or other sources or from a local research event. Potentially eligible patients interested in taking part of the study may therefore be referred from other sites.

The Investigator will keep records of all patients screened and included. The reason for screen failure should be stated for all patients screened but not included. The reason for withdrawal should be stated for all patients included but not completed.

Seventy Four (74) evaluable patients are required.

Patients who screen fail can be re-screened once depending on the reason for screen fail and as judged by the Investigator. The patient will then receive a new screening number.

4.2. Inclusion criteria

For inclusion in the study, patients must fulfil all the following criteria:

1. Male or female ≥ 18 and ≤ 79 years of age.
2. Signed a current Ethics Committee approved informed consent form.
3. Parkinson's disease, per UK Parkinson's Disease Society (UKPDS) Brain Bank Clinical Diagnostic Criteria.
4. Waking day dyskinesia of $>25\%$ determined as a score of ≥ 2 as per Question 4.1 of the MDS-UPDRS.
5. On a stable regimen of antiparkinson medications for at least 30 days prior to screening, including a levodopa preparation administered not less than three times daily and willing to continue the same doses and regimens during study participation. Rescue medication such as Madopar dispersable and Apomorphine injections are allowed.
6. Taking a maximum of eight regular levodopa intakes per day, excluding bedtime and night time levodopa.
7. Any other current and allowed prescription/non-prescription medications and/or nutritional supplements taken regularly must have been at a stable dose and regimen for at least 30 days prior to screening and the patient must be willing to continue the same doses and regimens during study participation (this criterion does not apply to medications that are being taken pre-study only on an as-needed basis).
8. Patient must be willing and able to avoid direct exposure to sunlight from day 1 to day 28.
9. Able to complete at least one valid 24-hour patient diary at Visit 1.

4.3. Exclusion criteria

Patients must not enter the study if any of the following exclusion criteria are fulfilled:

1. History of neurosurgical intervention related to Parkinson's disease (e.g. deep brain stimulation).
2. Treatment with pump delivered antiparkinsonian therapy (i.e. subcutaneous apomorphine or levodopa/carbidopa intestinal infusion).
3. History of seizures within two years prior to screening.
4. History of stroke or transient ischemic attack (TIA) within two years prior to screening.
5. History of cancer within five years prior to screening, with the following exceptions: adequately treated non-melanomatous skin cancers, localised bladder cancer, non-metastatic prostate cancer or in situ cervical cancer.

6. Presence of cognitive impairment, as evidenced by a Mini-Mental Status Examination (MMSE) score of less than 24 during screening.
7. A Hoehn and Yahr stage of five.
8. Any history of a significant heart condition or cardiac arrhythmias within the past 5 years, any repolarisation deficits or any other clinically significant abnormal ECG as judged by the Investigator
9. Severe or ongoing unstable medical condition including a history of poorly controlled diabetes; obesity associated with metabolic syndrome; uncontrolled hypertension; cerebrovascular disease, or any form of clinically significant cardiac disease, clinically significant symptomatic orthostatic hypotension; clinically significant hepatic disease, renal failure or abnormal renal function (definition of abnormal renal function is creatinine clearance <45 ml/min (calculated according to the Cockcroft-Gault formula).
10. Any history of a neurological other than Parkinson's disease or a psychiatric disorder, including history of DSM IV diagnosed major depression or psychosis. Patients with illusions or hallucinations with no loss of insight will be eligible. Patients with mild depression who are well controlled on a stable dose of an antidepressant medication for at least 4 weeks before screening will be eligible.
11. Enrolment in any other clinical study involving medication, medical devices or surgical procedures, current or within three months prior to screening visit, or previous participation in the present study. Patients enrolled in non-interventional clinical trials will be eligible.
12. Drug and/or alcohol abuse.
13. History of severe drug allergy or hypersensitivity.
14. If female, is pregnant or lactating, or has a positive pregnancy test result pre-dose.
15. Patients unwilling to use two forms of contraception (one of which being a barrier method see Section 7.3) 90 days for men and 30 days for women after last IMP dose
16. Any planned major surgery within the duration of the study.
17. Any other condition or symptoms preventing the patient from entering the study, according to the Investigator's judgement.

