1.7. Previous Clinical Studies

IRL790 has been investigated in two clinical studies, IRL790C001, a phase I randomised, double-blind, placebo-controlled, cross-over, single ascending dose (SAD) and multiple ascending dose (MAD) study in male healthy volunteers and IRL790C002, a phase 1b study of patients with advanced PD experiencing levodopa induced dyskinesia.

In the SAD part of IRL790C001, subjects were divided into two cohorts. Within each cohort the subjects were randomised to one of four treatment sequences, which included three dose levels of IMP. One of the dose levels was repeated once, taken with a standardised meal, all other doses were taken without food. In each of the six administered dose levels (5, 15, 40, 80, 120mg IRL790), six subjects received active drug and two subjects received matching placebo.

In the MAD part of this study, twenty-three subjects were treated with IMP. In the first cohort, nine subjects received IRL790, 40 mg/day for 10 consecutive days and three subjects received matching placebo. In the second cohort, nine subjects received IRL790, 80 mg/day for 10 consecutive days and three subjects received matching placebo.

Overall, IRL790 was well tolerated when given to healthy male subjects at single doses up to 120 mg and at multiple doses of 80mg per day for 10 days. The maximum tolerated dose was set to 120mg as a single dose and the maximal dose for multiple dosing was set to 80mg per day. Most of the treatment emergent (74%) AEs were of grade 1 intensity while 26% were of grade 2 intensity. The majority of AEs (48%) reported were considered as not related to study treatment while 11% were possibly related and 41% probably related. Overall treatment emergent AEs were mild, transient and possibly CNS related.

In agreement with preclinical findings, the pharmacokinetic evaluation in humans showed dose-linear kinetics with rapid absorption (average $T_{max} \approx 1$ h) and log-linear decline with a plasma half-life around 7h. Urine recovery data confirmed elimination from plasma occurred by a combination of renal excretion (fractional excretion around 35%) and metabolic degradation.

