4.4. Patient withdrawals

In all circumstances, patients will be made aware of the rights to refuse participation in a clinical trial and are entitled to freely withdraw their consent, without giving reasons. Patients will be assured that the withdrawal from the trial will not cause prejudice, will not result in any determinant and will not affect treatment. In addition, refusal to give consent or withdrawal of consent to participate in research will not lead to any liability or discrimination against the person concerned.

The Investigator has the right to withdraw patients from the study in the event of:

- Use of any non-permitted concomitant medication
- Non-compliance with the protocol and/or lack of willingness or commitment to cooperate in all phases of the study

- Protocol deviation
- Pregnancy after entry into study
- An adverse event which is considered intolerable by the patient
- Intercurrent illness that necessitates pharmacological treatment with a drug which interacts in any way with the test treatment
- Development of an exclusion criterion
- Treatment failure

Should a patient decide to withdraw for other reason, all effort will be made to complete and report observations as thoroughly as possible. A complete final evaluation at the time of withdrawal will be performed with an explanation of the exact reason why the patient is withdrawing from the study.

The Investigator is responsible for the optimal individual treatment of the patient.

The Investigator must fill in the “Study termination” section of the CRF explaining all reasons for withdrawal.

After a patient withdraws from a trial, the Investigator remains responsible for reporting SAEs considered causally related to the study drug. In addition, the Investigator must ensure appropriate treatment and follow-up of each adverse event ongoing at the time of the patient’s discontinuation.

In the event that a patient withdraws from the study for any reason other than an adverse event or other safety concern or is lost to follow-up within 30 days of treatment, the Principal Investigator may enrol a new patient to replace the withdrawn patient. The reason for the patient’s withdrawal from the study must be recorded.

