5.2. Non-permitted concomitant medications

All concomitant therapy used during and within four weeks prior to the study period must be recorded in the CRF. No other drug under investigation may be used concomitantly with the study medication.

Concomitant medications that are strong inhibitors of CYP2D6 should be avoided. As the elimination pathways of IRL790 regarding other CYP enzymes are unknown (except for CYP2A6, CYP2D6 and CYP3A4), there may be a risk of significant exposure increase when medications that are strong enzyme and transporter inhibitors are used together with IRL790. Strong inhibitors of these enzymes and transporters, including grapefruit juice, should be avoided throughout the study.

Examples of clinical inhibitors for P450-mediated metabolisms and clinical inhibitors for transporters⁸		
Isoenzyme (cytochrome P450)	Strong Inhibitors	Moderate Inhibitors
CYP1A2	ciprofloxacin, enoxacin, fluvoxamine, zafirlukast	methoxsalen, mexiletine, oral contraceptives
CYP2B6	-	-
CYP2C8	clopidogrel, gemfibrozil	deferasirox, teriflunomide
CYP2C9	-	amiodarone, felbamate, fluconazole, miconazole, piperine
CYP2C19	fluconazole, fluoxetine, fluvoxamine, ticlopidine	-
CYP2D6	bupropion, fluoxetine, paroxetine, quinidine, terbinafine	cimetidine, cinacalcet, duloxetine, fluvoxamine, mirabegron
Transporter	Inhibitor	
P-gp	amiodarone, carvedilol, clarithromycin, dronedarone, itraconazole, lapatinib, lopinavir and ritonavir, propafenone, quinidine, ranolazine, ritonavir, saquinavir and ritonavir, telaprevir, tipranavir and ritonavir, verapamil	
BCRP	curcumin, cyclosporine A, eltrombopag	

⁸ The list will be provided to the Investigator sites and maintained/updated throughout the study to provide information on clinical inhibitors for P450-mediated metabolisms and clinical inhibitors for transporters. Please note this is not an exhaustive and will be updated as new information becomes available and circulated to all sites.

OAT1B1, OATP1B3	atazanavir and ritonavir, clarithromycin, cyclosporine, erythromycin, gemfibrozil, lopinavir and ritonavir, rifampin (single dose), simeprevir
OAT1, OAT3	p-aminohippuric acid (PAH), probenecid, teriflunomide
MATE1, MATE2-K	cimetidine, dolutegravir, isavuconazole, ranolazine, trimethoprim, vandetanib

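### Exclusion criterion 10 admits patients on any stable antidepressant, Section 5.2 says to avoid three antidepressants as strong CYP2D6 inhibitors, and no eligibility criterion says which rule prevails.

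*Protocol*

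**What the plan says.** - **Protocol 4.3, criterion 10** (repeated in the synopsis) excludes most psychiatric history but then makes an exception that admits this group: "Patients with mild depression who are well controlled on a stable dose of an antidepressant medication for at least 4 weeks before screening". No drug or class is carved out.
- **Protocol 5.2**, under a heading that calls the drugs non-permitted, uses softer wording in the text: "Concomitant medications that are strong inhibitors of CYP2D6 should be avoided". It extends the advice on strong inhibitors to the whole study and gives the reason: "there may be a risk of significant exposure increase when medications that are strong enzyme and transporter inhibitors are used together with IRL790". The strong-inhibitor cell for CYP2D6 lists "bupropion, fluoxetine, paroxetine, quinidine, terbinafine".
- **Protocol 4.2, inclusion 7** covers other regular medication that is current and 'allowed'. It must have been stable for 30 days before screening, and "the patient must be willing to continue the same doses and regimens during study participation".
- **Protocol 4.4** gives the investigator a right, not a duty, to withdraw a patient. One of the listed grounds is "Use of any non-permitted concomitant medication".
- **Protocol 5.1** leaves other medication needed for the patient's safety or well-being to the investigator's discretion.

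**The concern.** A patient with mild depression on stable bupropion, fluoxetine or paroxetine satisfies the eligibility text while taking a drug that Section 5.2 asks sites to avoid. An investigator who enrols the patient and one who does not can each point to the protocol.

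Two things are at stake. The first is consistent eligibility across about 15 sites. The second is patient safety and the reading of dose and exposure on IRL790. In the phase 1b study (Protocol 1.7), five patients of the 11 randomised to IRL790 had transient worsening of parkinsonism during titration, which dose reduction mitigated, and two stopped for adverse events. Tolerability in this population therefore responds to dose. If a concomitant drug did raise exposure, it could add noise to the final-dose subgroups in SAP 4.10 and to the PK summaries by dose in SAP 7.4.

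**Working it through.** The plan gives no figure on this point, and the sample-size calculation does not enter into it. The check is a reading of the provisions against each other.

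1. **Overlap between the two rules.** The strong CYP2D6 cell in Section 5.2 holds five drugs. Three of them (bupropion, fluoxetine, paroxetine) are antidepressants; the table does not classify drugs by use, so this rests on general pharmacological knowledge. The overlap may be slightly wider, because fluvoxamine, also an antidepressant, is listed as strong for CYP1A2 and CYP2C19.

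2. **Criteria that could resolve it.** There are 9 inclusion and 17 exclusion criteria, 9 + 17 = 26. The number that cite Section 5.2 or exclude a user of a listed inhibitor is 0. The two nearest are:
   - Inclusion 7, which sets conditions on allowed drugs. It does not say that a patient taking a drug that is not allowed is ineligible.
   - Exclusion 17, the investigator's catch-all, which concerns conditions or symptoms and does not mention medication.

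3. **One patient traced through the text.** Take mild depression, well controlled on paroxetine at an unchanged dose for more than 30 days.
   - Criterion 10: eligible.
   - If paroxetine counts as allowed, inclusion 7 requires it to continue at the same dose. Section 5.2 says to avoid it throughout the study.
   - If it does not count as allowed, inclusion 7 is silent and criterion 10 still makes the patient eligible. Once the patient is in the study, Section 4.4 makes use of the drug a ground for withdrawal.
   - If it is stopped after Screening, the patient is arguably no longer controlled on a stable dose as criterion 10 describes. The protocol also states no interval between stopping and Day 1, and Screening may be as little as 7 days before randomisation.

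   No branch gives a single answer that all four provisions support.

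4. **When the conflict can be seen.** Concomitant medication is recorded at Screening (Section 7.2) and at Visit 1 (Section 7.3), and a footnote to Section 5.2 says sites receive the inhibitor list. The facts needed for a decision are therefore available before randomisation. What is missing is the rule to apply to them.

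5. **Size.** The documents do not give the share of IRL790 clearance carried by CYP2D6, the exposure increase under a strong inhibitor, or the expected number of antidepressant users.

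**The case against.** The best case for the plan is that criterion 10 is an exception to the psychiatric-history exclusion and not a licence for every antidepressant. Patients must meet all inclusion criteria, inclusion 7 speaks of allowed medication, and Section 5.2 is headed as non-permitted. Read together, mild depression is acceptable and the drug must still be allowed. That may well be the intention, but it is not written. Inclusion 7 regulates drugs that are allowed and bars nobody who takes another; 'should be avoided' is weaker than the heading above it; and Section 5.1 adds a discretion that points the other way.

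Several stronger readings are tempting, and the documents do not support them.

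- *That such patients will be randomised and then withdrawn.* Withdrawal under Section 4.4 is discretionary, and the medication record lets a site see the problem before randomisation.
- *That exposure will be raised by a known multiple.* Section 5.2 says only that there may be a risk. A reader might start from the "fractional excretion around 35" per cent in Section 1.7, take the remaining 65% as metabolic, assume CYP2D6 carries a fraction f of it and is fully blocked, and compute 1/(1 − 0.65f): 1/0.8375 = 1.19 at f = 0.25, 1/0.675 = 1.48 at f = 0.5 and 1/0.35 = 2.86 at f = 1. But f is nowhere given. The top figure needs CYP2D6 to carry all metabolism, although Section 5.2 also names CYP2A6 and CYP3A4 and one measured metabolite is acetylated. These values illustrate the formula and do not estimate the effect.
- *That the treatment comparison is biased.* Use of these drugs precedes randomisation, so users are balanced between arms in expectation, and the withdrawal ground applies to both arms. Flexible dosing and de-escalation for intolerance (Section 6.2) also respond to individual tolerability.
- *That 4 weeks in criterion 10 contradicts 30 days in inclusion 7.* Where both apply, the longer period governs.

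**Conclusion.** The inconsistency is real and visible in the text. Criterion 10 and Section 5.2 give different signals for users of three named antidepressants, and none of the 26 criteria explicitly resolves it. The supported consequences are that sites may decide differently on the same patient, and that a patient may be randomised while taking a drug for which the protocol acknowledges a possible exposure risk. That risk concerns only patients who receive IRL790. It can be confirmed from the protocol text, together with the general knowledge that the three drugs are antidepressants. Neither the exposure increase nor the number of patients can be derived from the documents, so the point carries no numerical effect on power, bias or safety. It is a cheap improvement, not a flaw in the primary analysis.

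**What to change.** The sponsor should reconcile criterion 10, inclusion 7, Section 5.2 and Section 4.4 so that one explicit answer on the strong inhibitors named in Section 5.2 applies before randomisation. The eligibility text should point to that answer, and sites should check it against the concomitant-medication record at Screening and Visit 1. The synopsis needs the same wording.

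The reconciliation should be confined to the strong inhibitors and should not tie eligibility to the whole Section 5.2 table. That table also lists moderate inhibitors, among them oral contraceptives under CYP1A2, which Section 7.3 accepts as part of contraception, so a blanket reference would create a new conflict. The wording should also make clear whether strong inhibitors in other rows, such as fluvoxamine, fall under the same rule. Which drugs are acceptable, and any interval after stopping one, is for the sponsor to decide.

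The cost is a wording amendment with no new data collection. Depending on the answer chosen, there may be a few more screen failures.

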4.4. Patient withdrawals

In all circumstances, patients will be made aware of the rights to refuse participation in a clinical trial and are entitled to freely withdraw their consent, without giving reasons. Patients will be assured that the withdrawal from the trial will not cause prejudice, will not result in any determinant and will not affect treatment. In addition, refusal to give consent or withdrawal of consent to participate in research will not lead to any liability or discrimination against the person concerned.

The Investigator has the right to withdraw patients from the study in the event of:

- Use of any non-permitted concomitant medication
- Non-compliance with the protocol and/or lack of willingness or commitment to cooperate in all phases of the study

- Protocol deviation
- Pregnancy after entry into study
- An adverse event which is considered intolerable by the patient
- Intercurrent illness that necessitates pharmacological treatment with a drug which interacts in any way with the test treatment
- Development of an exclusion criterion
- Treatment failure

Should a patient decide to withdraw for other reason, all effort will be made to complete and report observations as thoroughly as possible. A complete final evaluation at the time of withdrawal will be performed with an explanation of the exact reason why the patient is withdrawing from the study.

The Investigator is responsible for the optimal individual treatment of the patient.

The Investigator must fill in the “Study termination” section of the CRF explaining all reasons for withdrawal.

After a patient withdraws from a trial, the Investigator remains responsible for reporting SAEs considered causally related to the study drug. In addition, the Investigator must ensure appropriate treatment and follow-up of each adverse event ongoing at the time of the patient’s discontinuation.

In the event that a patient withdraws from the study for any reason other than an adverse event or other safety concern or is lost to follow-up within 30 days of treatment, the Principal Investigator may enrol a new patient to replace the withdrawn patient. The reason for the patient’s withdrawal from the study must be recorded.

4.4.1. Replacements

In the event that a patient withdraws from the study for any reason other than an adverse event or other safety concern, or is lost to follow-up within 30 days of treatment, a new patient will be enrolled to replace the withdrawn patient. The replacement will be managed through a centrally administered study wide randomisation list. The reason for the patient’s withdrawal from the study must be recorded.

5. CONCOMITANT MEDICATIONS

5.1. Permitted concomitant medications

Patients included in the study will be on stable anti-Parkinson treatment for at least 30 days prior to inclusion and during the study.

Other medications considered necessary for the patient’s safety and well-being may be given at the discretion of the Investigator.

